## 8 Documentation

Patients participating in the study will be monitored for:

Atrial Fibrillation, Mortality, Life threatening events, Physical impairment, Prolonged and additional hospitalisation.

Safety measures will include the following examinations:

Adverse Events, Vital Signs, Physical examination, ECG, Laboratory safety tests, Infection assessment, Inflammation screening.

In the event of procedure-related cardiac arrhythmias, ACC/AHA/ESC 2006 Practice Guidelines for management of subjects with ventricular arrhythmias and the prevention of sudden cardiac death will be implemented.

## 9 Statistical Analysis

### Power and sample size calculation

Two-sample test to determine whether the mean in group A,  $\mu_A$ , is different from the mean in group B,  $\mu_B$ . The hypotheses are

$$H_0: \mu_A - \mu_B = 0$$

$$H_1: \mu_A - \mu_B \neq 0.$$

Where the ratio between the sample sizes of the two groups is  $\kappa = n_A/n_B$

Formulas to compute sample size and power, respectively:

$$n_A = \kappa n_B \text{ and } n_B = (1 + 1/\kappa) * (\sigma^2 (z_{1-\alpha/2} + z_{1-\beta}) / (\mu_A - \mu_B))^2$$

$$1 - \beta = \Phi(z - z_{1-\alpha/2}) + \Phi(-z - z_{1-\alpha/2}), \quad z = (\mu_A - \mu_B) / (\sigma \sqrt{1/n_A + 1/n_B})$$

where

$\kappa = n_A/n_B$  is the matching ratio

$\sigma$  is standard deviation

$\Phi$  is the standard Normal distribution function

$\Phi^{-1}$  is the standard Normal quantile function

$\alpha$  is Type I error

$\beta$  is Type II error, meaning  $1 - \beta$  is power

utilizing the values:

Group 'A' mean,  $\mu_A = 20$  (estimates for mean TNF- $\alpha$  in pg/ml in treatment group)

Group 'B' mean,  $\mu_B = 30$  (estimates for mean TNF- $\alpha$  in pg/ml in sham group)

Standard Deviation,  $\sigma = 10$  (estimates for TNF- $\alpha$  standard deviation)

Sampling Size  $n_A = 20$  (treatment group size)

Sampling Size  $n_B = 20$  (sham group size)

Sampling Ratio,  $\kappa = n_A/n_B = 1$

Type I error,  $\alpha = 0,05$

calculates the Power,  $1-\beta = 0,8859$  which is an acceptable value.

For the statistical evaluation of the study data the software Graphpad Prism will be used. The evaluation of the double-blind data will be performed by a competent person utilizing appropriate statistical measures.

#### Primary Endpoint

Incidence of Atrial Fibrillation events in routine ECG following SOPs of clinical department of cardiac surgery.

#### Secondary Endpoint

Markers for IL-6, IL-10, CRP, TNF-alpha.

Utilizing paired t-Tests.

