## **7 Investigational Procedure**

Patients will be randomized double-blind into a treatment and sham group. Each group will consist of 20 Patients (please see "9 Statistical Analysis"). The follow-up covers the post-op hospital stay (approx 7-14 days). Inflammation markers will be assessed at day 0 (at device attachment), +2 and +7 days post device attachment. CRP, TNF-alpha, IL-6, and IL-10 will be assessed. Safety measures will include screening for and treatment of any occurring adverse events, vital signs, physical examination, ECG, 24-hour continuous ambulatory ECG, heart rate variability, laboratory safety tests, infection assessment, inflammation screen. In the event of procedure-related cardiac arrhythmias, ACC/AHA/ESC 2006 Practice Guidelines for management of subjects with ventricular arrhythmias and the prevention of sudden cardiac death will be implemented.

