## **10 Randomization**

The randomization procedure will be conducted utilizing the MUW randomizer (<https://www.meduniwien.ac.at/randomizer>) to achieve a 50% / 50% assignment of patients to the treatment and the sham group.

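### The markers, including the TNF-alpha that sets the sample size, are assigned to paired t-tests, although the plan states and powers a two-sample comparison of treatment with sham

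*Protocol*

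**What the plan says.** Three parts of the protocol bear on this.

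- **Section 9, Power and sample size calculation.** The hypotheses and the power are for a "Two-sample test to determine whether the mean in group A" differs from that in group B. The planning values are mean TNF-alpha of 20 pg/ml (treatment) and 30 pg/ml (sham), SD 10, 20 patients per group and type I error 0.05, with a stated power of 0.8859. The only other analysis statement there is general: "The evaluation of the double-blind data will be performed by a competent person utilizing appropriate statistical measures".
- **Section 9, Secondary Endpoint.** The endpoint is "Markers for IL-6, IL-10, CRP, TNF-alpha", and the method given is "Utilizing paired t-Tests". The entry does not say what is paired with what.
- **Sections 7 and 10.** On design: "Patients will be randomized double-blind into a treatment and sham group", with a randomizer used "to achieve a 50% / 50% assignment of patients to the treatment and the sham group". On sampling: "Inflammation markers will be assessed at day 0 (at device attachment), +2 and +7 days post device attachment".

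**The concern.** The power calculation and the Secondary Endpoint entry ask different questions of the same variable. The first asks whether mean TNF-alpha differs between treatment and sham. A paired t-test asks whether the mean of within-pair differences is zero. With two independent arms and repeated samples per patient, that becomes a question about change over time within an arm.

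Markers sampled in the days after heart surgery may change without any treatment effect; Table 1 of the protocol lists inflammation among the postoperative factors. The sham arm is there to remove such a shared change. A test of day 0 against a later day in the treated arm leaves it in. If that test were the analysis, a natural fall could not be told from an effect of stimulation, and the power that justifies 20 patients per arm would describe a test that the endpoint entry does not name.

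**Working it through.** **1. The plan's own figure.** Inputs from Section 9: difference 10 pg/ml, SD 10, n = 20 per arm, two-sided alpha 0.05.

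z = 10 / (10 × √(1/20 + 1/20)) = 3.162

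Power = Φ(3.162 − 1.960) + Φ(−3.162 − 1.960) = 0.885

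This agrees with the stated 0.8859 to within rounding. The exact two-sample t-test (noncentral t, 38 df, noncentrality 3.162) gives 0.869. Both figures belong to a comparison of treatment with sham.

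**2. What can be paired.** The protocol describes no matching and no crossover. The matching ratio in Section 9 is only the label for n_A/n_B. Pairing a treated with a sham patient would have no basis in the design. What remains is the same patient at two of the three sampling days, naturally day 0 against +2 or +7.

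**3. How a within-arm paired test behaves with no treatment effect.** SD 10 and n = 20 per arm are from the protocol. Three inputs are assumptions: within-patient correlation ρ of 0.3 to 0.7, the same SD on both days, and the same natural change d in both arms.

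SD of change = 10 × √(2(1 − ρ)), which is 11.8, 10.0 and 7.7 at ρ = 0.3, 0.5 and 0.7.

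Noncentrality = d / (SD of change / √20), with 19 df. For d = 5 and ρ = 0.5 it is 5 / (10/√20) = 2.236.

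Let p be the chance that the treated-arm test is significant. The sham arm has the same p independently, so the chance of treated significant and sham not is p(1 − p), which cannot exceed 25%.

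| Natural change d | p at ρ = 0.3 / 0.5 / 0.7 | p(1 − p) at ρ = 0.3 / 0.5 / 0.7 |
|---|---|---|
| 2.5 pg/ml | 15% / 19% / 28% | 12% / 15% / 20% |
| 5 pg/ml | 43% / 56% / 78% | 25% / 25% / 17% |
| 10 pg/ml | 95% / 99% / 100% | 5% / 1% / 0% |

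A two-sample t-test of the changes between arms, simulated at ρ = 0.5 with 40,000 trials, was significant in 5.1% (d = 5) and 5.0% (d = 10).

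**4. Power of a between-arm test for the planned 10 pg/ml, raw scale.** Adjusting for day 0 multiplies the SD by √(1 − ρ²), so the noncentrality is 3.162 / √(1 − ρ²), with 37 df.

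| Method | ρ = 0.3 | ρ = 0.5 | ρ = 0.7 |
|---|---|---|---|
| Unadjusted two-sample t-test | 0.87 | 0.87 | 0.87 |
| ANCOVA on the day-0 value | 0.90 | 0.94 | 0.99 |

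**The case against.** The strongest reply is that the protocol never says the sham arm will be ignored. Its null hypothesis is still that the two arm means are equal, and its general sentence on appropriate statistical measures leaves room for a between-arm test. A statistical analysis plan, not available here, may name one. A reader might infer from the paired tests that efficacy will be judged on within-arm change, or on significance in treatment but not in sham. No section states either rule, so that inference is not supported. The pairing of days within a patient is itself a deduction from the design.

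The size is also open. The protocol gives neither the correlation nor any natural change in the markers, nor the interval between surgery and device attachment. A change of 10 pg/ml equals the whole planning difference and serves only as illustration. At that change the treated-not-sham reading would rarely mislead (0-5%), because sham would be significant too. Finally, the markers are secondary.

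These limits stand, but they do not remove the contradiction. The general sentence names no test, while the Secondary Endpoint entry names one for these markers, and it is not the test that was powered. A later analysis plan can add detail, but it would have to override this text rather than complete it.

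**Conclusion.** The contradiction is in the protocol as written. One part of Section 9 states and powers a two-sample comparison of TNF-alpha; another assigns TNF-alpha and the other three markers to paired t-tests. On the only workable pairing, those tests do not estimate or test the randomised difference. The 0.8859 is reproduced for the two-sample test and does not apply to the paired one.

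The false-positive figures are conditional on the assumptions set out in the working. With no treatment effect, the treated-arm test is significant in 15-28%, 43-78% and 95-100% of trials for natural changes of 2.5, 5 and 10 pg/ml. If treated significant and sham not were read as an effect, the error rate would be 12-20%, 17-25% and 0-5%, against 5% for a between-arm test.

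The defect touches the secondary endpoint only; the analysis of atrial fibrillation is not affected. It still needs correcting, because TNF-alpha carries the trial's only sample-size justification.

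**What to change.** In Section 9, Secondary Endpoint, replace the paired t-tests with a between-arm comparison of each marker at days +2 and +7, adjusted for the day-0 value by ANCOVA, reported as the treatment-minus-sham difference with a 95% confidence interval. The minimum that resolves the contradiction is an unpaired t-test, as the power calculation already assumes. State that any within-arm paired tests are descriptive only.

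The change takes about one sentence and no new data, since day-0 samples are already scheduled. Under the planning values it loses no power. The drawback is that the adjusted model may need software other than the package named in Section 9. A log transformation, a mixed model over both days, and the choice of a leading marker and day are optional. The powers given here are for the raw scale and would not carry over to a log-scale analysis.

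### The four inflammation markers are set up for t-tests with no stated scale, and the TNF-alpha planning is in raw means; a log-scale between-arm comparison would probably gain a modest amount of power at little cost

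*Protocol*

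**What the plan says.** Section 9 of the protocol, under Power and sample size calculation, describes a "Two-sample test to determine whether the mean in group A" differs from that in group B. The inputs are TNF-alpha means of 20 ("in pg/ml in treatment group") and 30 in the sham group, one standard deviation of 10 for both, 20 patients per group and a two-sided alpha of 0.05. The stated power is 0.8859. No other marker has planning values.

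Under Secondary Endpoint the protocol lists "Markers for IL-6, IL-10, CRP, TNF-alpha" and adds only "Utilizing paired t-Tests". Section 7 fixes the sampling times: "Inflammation markers will be assessed at day 0 (at device attachment), +2 and +7 days post device attachment". No transformation, summary measure or rule for extreme or unmeasurably low values is given. Section 9 leaves the evaluation to be "performed by a competent person utilizing appropriate statistical measures".

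**The concern.** Hypotheses on arithmetic means in pg/ml, one SD for both arms and a t-test for every marker together describe a difference in raw means under a normal model. That model fits concentrations awkwardly. They cannot fall below zero, and a treatment that lowers levels in proportion would shrink the spread along with the mean, whereas a common SD of 10 implies a CV of 50% in the treatment arm (10/20) and 33% in the sham arm (10/30).

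If the values are right-skewed, a raw-mean test with 20 per arm gives much weight to a few high values and uses the samples less efficiently than a test on logs. TNF-alpha is the only endpoint with a stated power and the sole basis for the sample size, so power lost there matters even though the markers are secondary. If the scale is chosen only after the data are seen, the choice may also be influenced by the results.

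**Working it through.** **1. The plan's own figure.** z = (30 − 20) / (10 × √(1/20 + 1/20)) = 10/3.162 = 3.162. Power = Φ(3.162 − 1.960) = 0.885, which agrees with the stated 0.8859. The noncentral t version gives 0.869.

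**2. Skewed-data model (an assumption).** Lognormal values with mean m and CV c have log-scale SD s = √ln(1 + c²) and geometric mean m/√(1 + c²). For each scenario 40,000 trials were simulated with 20 per arm, and a two-sided 5% two-sample t-test was applied to raw and to log values. Arm means are 20 and 30 throughout. The common CV that matches a pooled SD of 10 is 10/√((20² + 30²)/2) = 10/25.5 = 0.39.

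| Scenario | Power, raw | Power, log | Gain (points) |
|---|---|---|---|
| CV 0.39 in both arms | 0.893 | 0.912 | 2 |
| CV 0.50 in both arms | 0.713 | 0.757 | 4 |
| SD 10 in both arms | 0.861 | 0.942 | 8 |
| CV 1.0 in both arms | 0.246 | 0.322 | 8 |
| CV 1.5 in both arms | 0.135 | 0.207 | 7 |

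Hand check of the log column at CV 0.50: s = 0.472; ln(1.5)/(0.472 × 0.3162) = 2.72; Φ(2.72 − 1.96) = 0.78 by the normal approximation, against 0.757 for the t-test.

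The SD 10 row flatters the log test. The geometric means there are 20/√1.25 = 17.9 and 30/√1.111 = 28.5, a ratio of 1.59 instead of 1.5.

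**3. No treatment effect.** The raw test rejects in 4.9% of trials at CV 0.5, 4.2% at CV 1.0 and 3.8% at CV 1.5. The log test rejects in 4.9 to 5.0%.

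**4. Change from day 0, compared between arms.** This needs a day-0 mean and a correlation, and the protocol gives neither. Follow-up means are 20 and 30, and both arms share the same day-0 mean.

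| CV | Correlation (log scale) | Day-0 mean | Power, raw change | Power, log ratio |
|---|---|---|---|---|
| 0.5 | 0.6 | 30 | 0.67 | 0.84 |
| 0.5 | 0.6 | 20 | 0.83 | 0.84 |
| 0.5 | 0.6 | 15 | 0.87 | 0.84 |
| 0.5 | 0.3 | 15 | 0.69 | 0.61 |
| 1.0 | 0.6 | 30 | 0.22 | 0.39 |
| 1.0 | 0.3 | 15 | 0.23 | 0.25 |

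At CV 0.5 the log scale gains 17 points, nothing, or loses a few, depending on the day-0 mean. At CV 1.0 and 1.5 it led in every combination of day-0 mean (15, 20, 30) and correlation (0.3, 0.6) that was run.

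**5. The paired test as literally named.** Within one arm of 20, with a fall from 30 to 20 and a log-scale correlation of 0.5, raw v log power is 0.92 v 0.95 at CV 0.5, 0.38 v 0.54 at CV 1.0 and 0.20 v 0.36 at CV 1.5. This test compares time points within patients. It does not compare treatment with sham.

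**The case against.** The strongest reply is that the protocol never says the markers are tested on the raw scale. A paired t-test can be run on log values, the wording on evaluation leaves room for it, and a statistical analysis plan that is not at hand may settle it. That is correct as far as it goes: the raw scale is an inference from the pg/ml hypothesis and the absence of any transformation. Only TNF-alpha is actually planned in pg/ml; IL-6, IL-10 and CRP are planned on no scale.

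Second, skewness is not documented. The one spread given implies mild skew, and on lognormal data with those values the raw test still has power 0.861, close to the noncentral t figure of 0.869. The stated power is therefore not undermined. A normal distribution with mean 20 and SD 10 does put 2.3% of patients below zero (two SDs below the mean), but the formula needs approximately normal sample means, not normal individual values, so that is no error in the calculation.

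Third, a reader might infer from the SD 10 scenario that the log scale gains 8 points, or from the change scores that it gains 17. Neither can be taken as the general result. The first includes a larger geometric-mean ratio, and the second requires a day-0 mean of 30 that the protocol does not state.

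What remains is that the protocol does choose a hypothesis on arithmetic means and a test family for all four markers, and that log analysis did better in every two-sample scenario run.

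**Conclusion.** The point holds as a cheap improvement to the secondary analysis. It is not an error that invalidates the plan. Read together, the two parts of section 9 describe a raw-scale analysis. Under an assumed lognormal shape, a between-arm log-scale test gains about 2 to 8 points of power at the TNF-alpha spread in the plan and 7 to 8 points at CVs of 100 to 150%, where both tests are weak. For change from day 0 the gain at a CV of 50% is uncertain in size and even in sign; at a CV of 100% or more the log scale led throughout.

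A reader might infer that a few extreme values will decide the marker results, or that the raw tests give false positives. The protocol contains no distributional data to support the first, and the null simulations contradict the second. The lognormal shape, the CVs above 50%, the correlations and the day-0 means are all assumptions.

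**What to change.** Under Secondary Endpoint in section 9, state that:

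- each of the four markers is log-transformed before analysis;
- treatment is compared with sham between arms, for example by the log day-7 value adjusted for the log day-0 value (this must be named, because a paired t-test does not compare arms; the power of this adjusted analysis was not computed here);
- the result is reported as a ratio of geometric means with 95% CI, with raw medians shown descriptively;
- values below the assay limit follow a rule fixed before unblinding.

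The change is to wording only, with no extra patients or samples. The drawbacks are that results read as ratios and not as pg/ml differences, and that low values near the assay limit gain influence on the log scale, so the rule for them matters.

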## **10 Randomization**

The randomization procedure will be conducted utilizing the MUW randomizer (<https://www.meduniwien.ac.at/randomizer>) to achieve a 50% / 50% assignment of patients to the treatment and the sham group.

## **11 Data Protection**

Participating patients are pseudonymized using an alphanumeric combination. Collected data are stored on a password-protected work PC in the room 20.E5.02.4. Access to personal data is only available to the sponsor / investigator [name] and by the sponsor authorized persons.

